#### **7.4.2 Concomitant Medications**

Concomitant medications are summarized by treatment regimen for the on-treatment and long-term follow-up periods. Medications are presented alphabetically by anatomic class, therapeutic class and generic name using the WHO dictionary.

Concomitant medications on treatment are those taken any time on or after the first dose of study therapy through the day preceding the earlier of the last dose of study therapy or open-label therapy. These also include prior medications with ‘continuing’ stop dates.

Concomitant medications during long-term follow-up are those taken on or after the day of last dose of study therapy. These also include on-treatment concomitant medications with ‘continuing’ stop dates.

Alternative anti-HBV medications are summarized separately for the long-term follow-up period.

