6.3.3 Medication Assessments

Medications taken within one month prior to study participation and while on study treatment will be reported. During the LTFU phase, anti-HBV medications will be reported.

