## 6 STUDY PERIODS, TREATMENT REGIMENS AND POPULATIONS FOR ANALYSES

### 6.1 Study Periods

Study periods for efficacy and safety analyses are defined as follows:

- **Pre-treatment period** begins at the first visit until initiation of study therapy.
- **On-treatment period** begins after the first day of study therapy and ends at the last dose of study therapy plus 5 days.
- **ETV treatment period** begins after the first day of active ETV and ends at the last dose of active ETV plus 5 days.
- **Off-treatment follow-up period** begins on the last dose of study therapy plus 6 days and ends at the start of alternative anti-HBV therapy minus 1 day.
- **Long-term follow-up period** begins on the last dose of study therapy plus 6 days until the end of the study.
- **Alternative ETV follow-up period** begins on the later of the last dose of study therapy plus 6 days and the start of alternative ETV therapy, until the end of the study.

Note that rescue open-label ETV is considered alternative anti-HBV therapy. See [Section 8.9](#) for additional conventions.

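### SAP 7.4.2 concomitant-medication windows do not match the SAP 6.1 study periods; on two of three readings, a medicine both started and stopped during open-label ETV is in no table

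*SAP*

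**What the plan says.** SAP 7.4.2 summarises concomitant medications for the on-treatment and long-term follow-up periods, then gives its own dates for each. A medicine is on-treatment if taken from the first dose "through the day preceding the earlier of the last dose of study therapy or open-label therapy". The second window reads: "Concomitant medications during long-term follow-up are those taken on or after the day of last dose of study therapy". The follow-up table also takes in earlier entries: "These also include on-treatment concomitant medications with" a stop date recorded as continuing. Alternative anti-HBV medicines get a separate follow-up summary. No separate open-label medication table is defined.

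SAP 6.1 sets different limits. The on-treatment period "begins after the first day of study therapy and ends at the last dose of study therapy plus 5 days", and long-term follow-up "begins on the last dose of study therapy plus 6 days until the end of the study". SAP 8.9 defines study therapy as blinded therapy or open-label ETV, so the 6.1 on-treatment period covers the open-label phase.

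On data collection, Protocol 6.3.3 has all medicines reported while on study treatment. For later use it says: "During the LTFU phase, anti-HBV medications will be reported". Protocol Table 6.1 agrees: the row for concomitant medication is blank in the LTFU column, and a separate row covers anti-HBV therapies.

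**The concern.** For a child who switches to open-label ETV, the on-treatment medication window appears to close near the switch at Week 52, while the follow-up window opens only at the last dose of study therapy. A course that begins and ends between those dates has no table to go into, although the protocol collects it.

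Readers use this table to judge whether co-medication could explain an ALT rise or another event on ETV. Adverse events and laboratory abnormalities are summarised through open-label ETV for the All ETV Safety Cohort (SAP 7.6, 7.6.5, 7.6.6.1), so the medication table would not cover the same period. Short courses are the ones at risk, and Protocol 5.5.1 permits up to 2 weeks of the listed nephrotoxic or hepatotoxic agents. Because such use is permitted, the prohibited-medication deviation list in SAP Appendix 1 may not show it.

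A separate matter is the follow-up table. With only anti-HBV medicines scheduled for collection in LTFU, many other entries may be there only because an earlier record was left as continuing.

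**Working it through.** The plan states no figure here to reproduce. The check is on date windows.

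**Inputs.** Open-label starts at Week 52 for Week 48 non-seroconverters (SAP 2.1). ETV stops at 96 weeks in total for subjects who never seroconvert. Open-label may run to Week 144 in the ETV arm and Week 192 in the placebo arm (SAP 2.1). Placebo non-seroconverters are taken to about Week 144.

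**Step 1: three readings of the 7.4.2 end date.**
- A: the day before the first open-label dose.
- B: the day before the last open-label dose. Under 8.9 this is also the last dose of study therapy for a switched subject, so the two dates coincide and *earlier of* does nothing.
- C: study therapy taken to mean blinded therapy only, giving the day before the last blinded dose.

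**Step 2: test medicines in a subject who switches at Week 52.**

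| Medicine taken | A or C | B | Limits of 6.1 |
|---|---|---|---|
| Weeks 20–22 | on-treatment | on-treatment | on-treatment |
| Weeks 50–60 | on-treatment | on-treatment | on-treatment |
| Weeks 60–62 | **neither table** | on-treatment | on-treatment |
| Week 60, still continuing at end | follow-up only | both | both |
| Last dose +2 to +4 days | follow-up | follow-up | on-treatment |

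Row three is the gap. Row four is misplacement, not loss. Row five is the boundary mismatch: the last-dose day and the next 5 days, 1 + 5 = 6 days, fall in different periods in the two sections whichever reading is taken.

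**Step 3: time exposed to the gap under A or C.** Share = (stop week − 52) / stop week.
- ETV, never seroconverts: (96 − 52)/96 = 44/96 = 46%.
- ETV, seroconverts at Week 96: (144 − 52)/144 = 92/144 = 64%.
- Placebo, non-seroconverter: about 92/144 = 64%.
- Placebo, treated to Week 192: (192 − 52)/192 = 140/192 = 73%.

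**Step 4: who is exposed.** Protocol 8.1 expects 18 placebo subjects from the first accrual year to reach Week 48 and, at 10% seroconversion, 18 × 0.9 = 16.2, so 16, to switch. Week 48 seroconverters who remain on blinded therapy have no open-label phase and no gap.

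**The case against.** The strongest reply is that the gap is not established. SAP 7.4.2 never says first dose or start of open-label therapy, and SAP 7.6 says so explicitly when it means that cut. The phrase can be read as the last dose of either therapy, which is reading B and leaves no gap. This stands as far as it goes: the text is ambiguous. But reading B makes *earlier of* redundant, and it still leaves the 6-day mismatch, so the wording needs correction either way.

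A reader might infer that every medicine started in open-label is lost. It is not: anything still taken on or after the last dose enters the follow-up table, and anything begun before the switch is counted on-treatment. A reader might also infer that all placebo children are affected, but those who seroconvert at Week 48 stay on blinded therapy.

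It is equally tempting to say that the follow-up table holds nothing but carry-forward. It also holds the anti-HBV medicines collected in LTFU and any medicine with a recorded stop date on or after the last dose. Treatment given for an adverse event is recorded on the CRF (Protocol 7.3), and concomitant use is checked at the End of Treatment visit (Protocol Table 6.1). The carry-forward rule is openly stated. What remains is that the table does not distinguish confirmed use from an open stop date.

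There is also real mitigation: prohibited medicines are listed as on-treatment deviations, alternative anti-HBV therapy has its own follow-up summary, and ALT flares are plotted by subject.

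**Conclusion.** The concern holds as a conflict between SAP 7.4.2 and SAP 6.1 with 8.9. The 6-day mismatch at the end of treatment is certain. The open-label gap is likely rather than certain: it follows from both readings that give the sentence's comparison any effect, and it is confined to medicines both started and stopped during open-label ETV.

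The exposed share of treatment time runs from 46% to 73% by treatment path, assuming the switch at Week 52 and treatment to the planned stop. These are shares of time, not of medicines; the documents give no basis for counting how many courses would be missed.

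The consequence is an incomplete descriptive safety table, mainly in the analyses after the primary one. SAP 9 calls there for all analyses in the plan, with exceptions that do not name the open-label medication summary. No efficacy test changes. The documents do not support a claim that the data are lost, since the protocol still collects them, or that the follow-up table must be removed. This is a minor point, worth making because the correction is almost free.

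**What to change.** In SAP 7.4.2:
- Define on-treatment concomitant medication as any medicine taken from the first dose through the last dose of study therapy, blinded or open-label, plus 5 days. Split it into blinded and open-label phases if wanted.
- Start follow-up medication at the last dose plus 6 days. Stopping on-treatment at the last dose itself would leave the mismatch with 6.1.
- Keep the follow-up table, but flag as carried forward any non-anti-HBV entry that is there only through a continuing stop date.

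SAP 8.9 dates alternative anti-HBV therapy partly from medication taken on treatment. A cross-reference to 6.1 there would settle which definition applies.

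Under these windows the Week 60–62 course falls in the on-treatment table. The cost is a few lines of SAP wording, a changed date filter and one flag. No new data are needed and no table is dropped.

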### **7.5 Efficacy**

Efficacy endpoints are presented by as-randomized treatment regimen for treated subjects.

Binary efficacy endpoints are analyzed using 2 algorithms:

- Non-Completer = Failure (NC = F): The numerator is based on subjects meeting the response criteria. The denominator is based on treated subjects. Subjects who have missing data at the analysis week are considered as failures.
- Non-Completer = Missing (NC = M): The numerator is based on subjects meeting the response criteria. The denominator is based on subjects with data at the analysis week. Subjects who have missing data at the analysis week are excluded.

Treatment regimens are compared using a difference in proportions (ETV - PBO), 95% confidence interval (CI) and p-value based on  $NC = F$  for the primary endpoint and key secondary endpoints. Analyses are stratified by age randomization strata (see [Section 7.3.4](#)). The proportions are computed within each stratum, and combined using a weighted average with weights proportional to stratum size (Cochran-Mantel-Haenszel [CMH] weighting). ETV will be considered superior to PBO if the p-value is  $< 0.05$ . CIs for differences in proportions are based on the stratified normal approximation to the binomial distribution with unpooled proportions used in the computation of the standard error of the difference.

A two-stage testing procedure will be employed for testing the primary and key secondary endpoints using  $NC = F$ . In the first stage, the test for primary endpoint will be performed. Provided the test result of the primary endpoint is significant (p-value  $< 0.05$ ), the second stage tests of the key secondary endpoints will be conducted. Because the tests for the key secondary endpoints will be conducted sequentially only if the test for the primary endpoint is successful, significance levels will not be adjusted for the first stage testing. All tests for treatment comparison will be two-sided at a significance level of 0.05.

For binary composite endpoints involving several components (eg, primary efficacy endpoint), only subjects who meet the response criteria for all components are considered to be responders for the composite endpoint. In addition, subjects who meet the response criteria for some components but are missing other components are considered to be missing the composite endpoint.

See also [Sections 8.4 to 8.8](#) for additional conventions.

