8 STATISTICAL CONSIDERATIONS

8.1 Sample Size Determination

One hundred and twenty-three (123) subjects (randomized 2:1 to ETV vs placebo) in this study will provide 90% power to show superiority of ETV versus placebo assuming a response rate for the primary endpoint HBV DNA by PCR < 50 IU/mL (approximately 300 copies/mL) and HBeAg seroconversion of 20% for ETV arm and 1% for placebo arm. A two-sided significance level of 0.05 will be used. Subjects who either discontinue from study treatment prior to Week 48 or have having missing Week 48 HBV DNA or HBeAg serology measurement will be considered as failures at Week 48 (Non-Completer = Failure). The efficacy estimate for ETV is derived from an analysis of the identical endpoint (HBV DNA by PCR < 300 copies/mL and HBeAg seroconversion) in the pivotal Phase 3 study of HBeAg-positive subjects, (AI463022). The efficacy estimate for the placebo arm is derived from evidence in the literature which shows that whereas spontaneous seroconversion occurs at a relatively high rate in children, viral replication remains detectable using sensitive PCR assays. The results of the Gilead Sciences' pediatric CHB study (GS 518)¹³ support this estimate; 3 of

57 placebo treated subjects (5.3%) achieved HBeAg seroconversion, but only 1 of 58 subjects (1.7%) achieved HBV DNA < 2.23 log copies/mL at Week 48.

This sample size will also fulfill the requirement that the ETV integrated pediatric safety database has at least 100 pediatric patients who have received ETV for at least 48 weeks; this database will be comprised of subjects currently enrolled in study AI463028 and from this study (AI463189). Currently 24 nucleoside naive subjects are enrolled in AI463028; all 24 would have had 48 weeks of safety data collection by the time study AI463189 reaches Week 48.

Based on the original planning for study AI463189, it is estimated that 175 subjects will be enrolled to have approximately 123 subjects randomized (approximately 30% screen failure rate). Randomization will be 2:1 (ETV 82: Placebo 41); assuming a 10% drop out rate per year and even enrollment for 2 calendar years, approximately 72 ETV randomized subjects will have 48 weeks of safety data by study Week 144. This brings to approximately 96 the number of subjects that will be included in the integrated safety database at the end of study Week 144.

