Additional safety data will be contributed by placebo randomized subjects switching to open-label ETV by study Week 52. Because it is expected to take 2 calendar years to randomize 123 subjects, and assuming even enrollment over that time frame, the last placebo randomized subject will be completing Week 48 by study week 144. Assuming a 10% drop out per year, 18 of the 20 subjects randomized to PLB during the first calendar year will reach Week 48 by study Week 96; 16 of these 18 will be switched to open-label ETV (assuming a 10% HBeAg seroconversion rate on the PLB arm). With a 10% drop out rate per year, 14 of these 16 will be completing 48 weeks of open-label ETV by study Week 144 and will be added to the integrated safety database. This will bring the number of patients in the integrated safety database to approximately 110 subjects with at least 48 weeks of ETV exposure by study Week 144.

While the analysis of the primary endpoint is based on a randomized sample size of 123, the size of the overall study population has been augmented to 180 randomized subjects in order to meet the requirement of a health authority. Therefore the final safety dataset as described in the previous 2 paragraphs will also be augmented. The accrual of the first 123 randomized subjects is expected to take 2 years. Thereafter, the enrollment will

remain open until 180 subjects are randomized. Additional re-analyses will be performed on the augmented population.

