8.4 Analyses

Binary variables will be summarized by counts and percentages. Comparisons of binary variables will be based on Cochran-Mantel-Haenszel (CMH) statistic stratified by age group. Confidence intervals (CI) for differences in proportions will be based on the normal approximation to the binomial distribution with unpooled proportions used in the computation of the standard error of the difference. The CI procedure will be used for both primary and secondary efficacy endpoints if applicable.

Continuous variables will be summarized with univariate statistics (eg, mean, median, standard deviation, minimum, and maximum).

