### **7.5.2 Key Secondary Endpoints**

The tests of the key secondary endpoints are conducted sequentially in the order specified below, provided the test result of the primary endpoint is significant. The  $n$ th key secondary endpoint is tested provided the test result of the  $(n-1)$ st key secondary endpoint is significant ( $n = 1, 2, \dots, 5$ ).

Treatment regimens are compared (ETV - PBO) with a difference in proportions and p-value at Week 48 on treatment for the Primary Cohort at the primary analysis (see [Sections 6.3](#) and [9](#)) using  $NC = F$ , unless specified otherwise.

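### The planned unpooled confidence interval does not match the protocol's CMH test, and the SAP does not name the test behind its p-value

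*SAP*

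**What the plan says.** Protocol 8.4 sets the test and the interval in one paragraph. On the test: "Comparisons of binary variables will be based on Cochran-Mantel-Haenszel (CMH) statistic stratified by age group". On the interval: "normal approximation to the binomial distribution with unpooled proportions used in the computation of the standard error of the difference". It applies this interval to the primary and secondary efficacy endpoints where applicable. Protocol 8.4.3 and the synopsis repeat the normal approximation.

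SAP 7.5 reports a difference, a 95% interval and a p-value for the primary and key secondary endpoints. The stratum proportions are "combined using a weighted average with weights proportional to stratum size", which the SAP calls CMH weighting, and the interval is the one cited from Protocol 8.4: "CIs for differences in proportions are based on the stratified normal approximation to the binomial distribution with unpooled proportions". It names no test. CMH appears there only as a label for the weights.

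Both documents declare superiority on p < 0.05. In SAP 7.5.2, "The tests of the key secondary endpoints are conducted sequentially in the order specified below", each conditional on the one before. HBeAg seroconversion is fourth. Neither document says how an interval and a p-value that disagree would be reported.

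**The concern.** A CMH test and an unpooled interval use different variances. When groups are equal in size the difference is usually small. Here allocation is 2:1 and the higher response rate is expected in the larger arm, which makes the unpooled standard error systematically smaller than the null one. A results table could then show an interval clear of 0 beside a non-significant p-value. This would arise mainly on the primary endpoint and on HBeAg seroconversion, where the expected rates are low.

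What is at stake is the reported interval and how readers interpret it. A second issue follows from the SAP's silence: the p-value that decides superiority and opens the testing sequence comes from a test the SAP does not identify.

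**Working it through.** **Inputs.** Arm sizes of 82 and 41, primary-endpoint rates of 20% and 1%, and two-sided 0.05 come from Protocol 8.1. Placebo HBeAg seroconversion is 5.3% (3 of 57 in the cited pediatric study) or 10% ("assuming a 10% HBeAg seroconversion rate on the PLB arm"), both also from Protocol 8.1. The ETV seroconversion rate is not given. It cannot be below the planned 20% composite rate, because seroconversion is one component of the composite. I assume 20–30% and also show 35%.

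**Step 1: reproduce the plan's sample size.**
- Pooled rate = (82 × 0.20 + 41 × 0.01)/123 = 0.1367.
- Null SE = √[0.1367 × 0.8633 × (1/82 + 1/41)] = 0.0657.
- Unpooled SE = √[0.20 × 0.80/82 + 0.01 × 0.99/41] = 0.0468.
- Power with a null-variance test = Φ[(0.19 − 1.96 × 0.0657)/0.0468] = Φ(1.31) = 90.4%. This matches the stated 90% at 123 subjects.
- With the unpooled SE throughout: Φ(0.19/0.0468 − 1.96) = 98.2%.

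The stated figure therefore fits a null-variance test of the CMH type.

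**Step 2: size of the mismatch.** The ratio of unpooled to null SE is 0.0468/0.0657 = 0.71 at 20% versus 1%, and 0.78–0.90 at the HBeAg rates. With 62:61 allocation the same ratios would be 0.94 and 0.94–0.99. Allocation is the main cause. Few placebo responders add to it.

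**Step 3: two data sets.**
- 7/82 versus 0/41, unstratified. The difference is 0.0854 and the unpooled SE is √(0.0854 × 0.9146/82) = 0.0309, so the interval is 2.5% to 14.6%. CMH p = 0.055.
- 16/82 versus 3/41, split 5, 5, 6 and 1, 1, 1 over strata of 27/27/28 and 14/14/13. The planned interval is 0.5% to 23.9%. CMH p = 0.083.

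**Step 4: how often.** Simulation with those strata, 200,000 trials per row, CMH without continuity correction:

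| ETV vs placebo | CI excludes 0, CMH not significant | Of these, CMH p 0.05–0.10 | Planned coverage | Score coverage |
|---|---|---|---|---|
| 20% vs 1% (primary) | 3.4% | 88% | 94.4% | 96.7% |
| 20% vs 5.3% | 13.3% | 94% | 94.3% | 95.4% |
| 20% vs 10% | 11.6% | 96% | 93.8% | 95.0% |
| 25% vs 5.3% | 7.0% | 98% | 94.3% | 95.4% |
| 25% vs 10% | 11.5% | 99% | 93.8% | 94.9% |
| 30% vs 5.3% | 2.7% | 99% | 94.3% | 95.3% |
| 30% vs 10% | 7.9% | 99.6% | 93.9% | 94.9% |

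In these rows the reverse conflict is essentially absent. Exact unstratified enumeration also gives 3.4% for the primary endpoint, and uneven strata change little. At 35% ETV the disagreement falls to 0.7% (placebo 5.3%) or 3.9% (placebo 10%). Under 1:1 allocation it would be 0.4–0.8% for the primary endpoint.

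**Step 5: where the interval errs.** At the assumed HBeAg rates the planned lower limit lies above the true difference in about 3–4% of trials, against a nominal 2.5%. The score interval described in Step 7 brings this to just over 2%.

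**Step 6: the other reading of SAP 7.5.** If the p-value came from the unpooled SE, interval and p-value would agree. Two-sided rejection when both arms share a rate would be:

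| Common rate | Unpooled SE as test | CMH |
|---|---|---|
| 1% | 0.7% | 2.8% |
| 3% | 7.2% | 3.9% |
| 5.3% | 8.5% | 3.7% |
| 10% | 6.9% | 4.6% |

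**Step 7: does a matched interval remove the conflict?** Take stratum weights w = n₁n₀/N and multiply the score variance by N/(N−1). With m responders in a stratum, at a difference of 0:
- the numerator Σw(p₁ − p₀) equals Σ(x₁ − n₁m/N);
- the variance equals Σ n₁n₀m(N−m)/[N²(N−1)].

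Both are the CMH quantities, so agreement is exact, and simulation found no disagreement. In the second example of Step 3 this interval is −1.9% to 23.7%. Without the N/(N−1) factor, 0.2–1.2% disagreement remains. Against a continuity-corrected p-value it would be 4–14%.

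**The case against.** **The SAP may not use CMH at all.** SAP 7.5 lists difference, interval and p-value under one weighting scheme, so the p-value could share the interval's standard error. This stands as far as it goes: the conflict arises only when Protocol 8.4 and SAP 7.5 are read together. But that reading would depart from the protocol's stated test and carry the error rates in Step 6. On either reading the test needs to be named.

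**No decision depends on the interval.** Correct. Both documents make p < 0.05 the criterion, so a rule of precedence largely exists. A reader might infer that an interval excluding 0 could support a superiority claim or open the next test; the documents do not allow that. A reader might also infer that the plan inflates type I error. That would need the unpooled reading and common rates of about 3–10%. At the planned 1% placebo rate there is no inflation, and under CMH there is none at the rates examined.

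**The HBeAg range rests on an assumed rate.** It does. The 13% end requires essentially every ETV seroconverter also to have HBV DNA below 50 IU/mL. The 30% upper end has no source in the documents, and higher rates shrink the problem. The figures are also unconditional, although conditioning on a significant primary test barely moves them (2.2–13.4%).

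**The replacement is a trade-off.** At 20% versus 1%, the one fully specified scenario, planned coverage (about 94.5%) is nearer 95% than the score interval's 96.7%. That stands. The score interval is closer at the assumed HBeAg rates.

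**Conclusion.** The point holds as a minor one. If the p-value is the protocol's stratified CMH test, the planned interval excludes 0 beside a non-significant p-value in about 3.4% of trials for the primary endpoint at the planned rates. For HBeAg seroconversion it is about 3–13% under an assumed ETV rate of 20–30%, and less above that. Most of these cases are borderline, with CMH p between 0.05 and 0.10. If the p-value instead uses the unpooled SE, the conflict disappears, but the test departs from the protocol and is anti-conservative at common rates of 3–10%.

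It would go too far to say that the SAP itself pairs two different variances, because it names no test. It would also go too far to say that any efficacy conclusion is at risk. The sample size stands. What can be improved is the specification of the test, the lower limit of the interval and its consistency with the p-value.

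**What to change.** 1. In SAP 7.5, name the age-stratified CMH test without continuity correction as the source of the p-value.
2. In SAP 7.5, and in Protocol 8.4, 8.4.3 and the synopsis, replace the unpooled interval with a stratified Miettinen–Nurminen score interval. Use stratum weights n₁n₀/N and the N/(N−1) variance factor. Because the protocol prescribes the present interval, this needs an amendment or a documented change to the planned analysis; editing the SAP alone would make the two documents contradict each other.
3. If the present interval is kept, still name the test, and state that the CMH p-value governs where the two differ.

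**Cost.** Wording in two documents and one programming change. The CMH p-value, its power (about 95% at 20% versus 1%) and the sample size do not change. Downsides:
- Intervals widen by about 2–3 points: 17.9 to 20.6 at 20% versus 1%, 21.3 to 23.8 at 20% versus 5.3%, and 26.1 to 27.8 at 30% versus 10%.
- Coverage is slightly conservative at 20% versus 1%.
- The new weights equal the SAP's only when every stratum is exactly 2:1. The point estimate moves by 0.1 point on average at 27/27/28 versus 14/14/13. It moves by 0.2–0.4 on average (at most 2.6) if strata are assumed to be off 2:1 by two or three subjects.
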